#### Inclusion:

[figure not shown]
Those subjects who sign and date the informed consent document, meet all of the study eligibility criteria, and are approved by the Independent Reviewer will be eligible for inclusion into the Valiant Evo International Clinical Trial. The subject will only be considered included when arterial access is established and an attempt to introduce the Valiant Evo Thoracic Stent Graft is made.

Included subjects will be documented on the Screening, Enrollment and Inclusion log and will be followed per the study protocol. Subjects who are enrolled and attempted to be implanted with the device but the Valiant Evo Thoracic Stent Graft could not be implanted during the procedure (treatment failure) will be followed through the 1 month follow-up per the study protocol and thereafter as per hospital standard of care. Serious Adverse Events will be collected for these subjects over the whole duration of the study. The reason for not including the subjects into the trial will be documented on the Screening, Enrollment and Inclusion log and will be documented on the screening eCRF.

The investigator will maintain a log of all subjects screened, enrolled, and included in the clinical study, assigning an identification code linked to their names, alternative subject identification or contact information.

As the point of enrollment is considered the point in time the subject signs and dates the Informed Consent Form, which is different from the point that the subject is actually included in the trial, more subjects will be enrolled in the trial than included. A 10 to 20% screen failure rate is expected. Therefore, approximately 57 subjects are expected to be enrolled in order to include 47 subjects.

\* The subject will only be considered included when arterial access has been established with an attempt to introduce the Valiant Evo thoracic stent graft.  
**Note:** A patient withdrawing informed consent stops the process on the date of withdrawal.

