	
related aneurysm rupture (i.e., perforation of the aneurysm during the course of the implantation procedure) or as a late aneurysm rupture that follows device deployment.
 
Excluded are aneurysms in anatomic areas other than the targeted segment treated by the Valiant Evo Thoracic Stent Graft System.

Aneurysm expansion	Aneurysm maximum diameter increase > 5 mm as compared to the 1- month contrast enhanced imaging measurements
Stent graft migration	
Evidence of proximal or distal movement of the stent graft (>10 mm) relative to fixed anatomic landmarks (e.g. supra aortic trunks, coeliac trunk), which is not due to remodeling of the subject's vasculature.
 
The 1-month imaging will be used as the baseline for this determination.

Loss of stent graft patency	Defined as a 100% complete blockage (occlusion) of the lumen diameter of any implanted stent graft component(s) as evidenced by CT, angiography, ultrasound, or other appropriate imaging modality, and/or operative pathological analysis.
Endoleak	
Defined by the presence of contrast-enhanced blood outside the lumen of the endoluminal graft but within the aneurysm sac. Endoleaks are classified as follows:
 
Type I a – Leak at the proximal graft attachment site
 
Type I b - Leak at the distal graft attachment site.
 
Type I c - Leak around a fenestration, branch end point, or branch occluding plug (e.g., plug occluding a subclavian artery or iliac artery to prevent flow into an aneurysm sac).
 
Type II – Retrograde flow from branch arteries arising from the excluded segment.
 
Type III a – Endoleak between the segments of the modular graft (junctional endoleak).
 
Type III b – Endoleak in the mid-graft region due to the defect of fabric.
 
Type IV – Transgraft leak due to fabric porosity.
 
Type V – Aneurysm enlargement in the absence of any demonstrable perfusion of the aneurysmal sac
 
Type undetermined - Endoleak of undefined origin

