7.1.3. Analysis Sets

Analysis set to be used for each endpoint analysis will consist of all subjects who were enrolled. The subject will only be considered enrolled when arterial access is established and an attempt to introduce the Valiant Evo Thoracic Stent Graft is made.

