- Aneurysm-Related Mortality within 365 days
- MDEs within 365 days
- All AEs within 365 days including:
 - MAEs
 - SAEs
- Secondary procedures within 365 days
- Loss of stent graft patency within 12 months based on imaging findings
- Endoleaks at 12 months based on imaging findings
- Stent graft migration at 12 months as compared to 1-month imaging
- Aneurysm expansion > 5mm at 12 months based on imaging findings relative to the 1-month visit

Secondary endpoints are to be assessed beyond 12 months. The following secondary endpoints are to be evaluated at 24, 36, 48, and 60 months:

- All-cause mortality
- Aneurysm-Related Mortality
- MDEs
- All AEs and SAEs
- Secondary procedures
- Loss of stent graft patency based on site reported imaging findings
- Endoleaks based on site reported imaging findings

- Stent graft migration as compared to 1-month imaging
- Aneurysm expansion > 5mm based on site reported imaging findings relative to the 1-month visit

Health-related quality of life outcomes are to be assessed at all scheduled follow-up visits using the EQ-5D questionnaire.

Stent graft migration will be determined by the core lab or site imaging case report from (CRF). Core lab assessment and site reported result will be analyzed separately. Aneurysm expansion will be calculated. When 1-month image is not available, the latest image taken prior to 1-month will be used for calculation.

Descriptive statistical analyses will be performed on secondary endpoints. No inferential statistical analysis is planned for secondary endpoints.

Non-image endpoints event rates such as mortality, secondary procedures, MAEs, SAEs, conversion to open surgery, and thoracic aortic aneurysm ruptures through 1 year will be calculated in the same way as the MDE rate, specified in Table 5. The event rates beyond 1 year through 5 years will be analyzed using Kaplan Meier method.

Imaging based Event Rate Calculation:

Unless otherwise specified, imaging assessment will be performed by site as well as the core lab. Assessments from the core lab will be the primary result for the PMA and PMA-s submissions and analyzed separately from those by site. Imaging based event rate will be calculated using statistical analysis windows as follows (Table 6):

Table 6: Imaging based Event Rate Calculation:

Event rate = m/n	At 1 Month	At 6 Months	At 12 Months

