m = No. of Subjects Who Had Event(s)	No. of subjects who had an event with scan day within the 1-month window.	No. of subjects who had an event with scan day within the 6-month window.	No. of subjects who had an event with scan day within the 12-month window.
n = No. of Subjects Who Had Readable Images	No. of subjects who had a readable image within the 1-month window.	No. of subjects who had a readable image within the 6-month window.	No. of subjects who had a readable image within the 12-month window.
Event rate = m/n	Through 1 Month	Through 6 Months	Through 12 Months
m = No. of Subjects Who Had Event(s)	No. of subjects who had an event with scan day within the 1-month window.	No. of subjects who had an event with scan day within 1- or 6-month windows.	No. of subjects who had an event with scan day within 1-, 6- or 12-month windows.
n = No. of Subjects Who Had Readable Images	No. of subjects who had a readable image within the 1-month window.	No. of subjects who had an event (counted in m) or had a readable image within the 6-month window.	No. of subjects who had an event (counted in m) or had a readable image within the 12-month window.

The imaging based event rates by visit at 24, 36, 48 and 60 months will be calculated in a similar way as above; i.e., m = number of subjects who had an event with scan day within the statistical analysis window of the specific time point; n = number of subjects who had a readable image within the 12-month window.

The cumulative event rate through 24, 36, 48 and 60 months will be estimated using survival analysis. Kaplan-Meier estimates, along with its standard error using the Greenwood method, will be reported for non-image based events. The image-based events are interval censored data and the interval censored survival analysis method will be used to calculate the event rates.

When reporting the site reported endoleaks, both site imaging findings and the events treated during secondary procedures will be accounted for in the analysis.

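### SAP Table 6 uses one imaging denominator for all endpoints, so subjects with no usable baseline count as free of migration, and at 1 month subjects with no graft count as free of endoleak and patency loss

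*SAP*

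**What the plan says.** **Rate.** SAP 7.9, Table 6, defines an image-based rate as m/n. In the At 12 Months column m is "No. of subjects who had an event with scan day within the 12-month window" and n is "No. of subjects who had a readable image within the 12-month window". The 1- and 6-month columns follow the same pattern. The table does not vary by endpoint.

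**Analysis set.** SAP 7.1.3: "Analysis set to be used for each endpoint analysis will consist of all subjects who were enrolled". Enrolment does not require an implanted graft: "The subject will only be considered enrolled when arterial access is established and an attempt to introduce the Valiant Evo Thoracic Stent Graft is made".

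**Migration.** The SAP endpoint is "Stent graft migration at 12 months as compared to 1-month imaging". Protocol L.2.1 says the same in its definition: "The 1-month imaging will be used as the baseline for this determination". SAP 7.9 makes migration a call by the core lab or on the site imaging form. Aneurysm expansion, by contrast, is calculated, and the sentence after that lets the most recent image before 1 month stand in for a missing 1-month image in the calculation.

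**Subjects without a graft.** Protocol F.1 says that subjects in whom implantation was attempted but not achieved "will be followed through the 1 month follow-up per the study protocol and thereafter as per hospital standard of care". Protocol F.2.4 lists contrast CT/MRI among the procedures at every required follow-up visit, including 1 month. Protocol L.2.1 defines endoleak relative to the lumen of the graft, and loss of patency as occlusion of an implanted component.

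**The concern.** A proportion is interpretable when everyone in n could have been counted in m. Table 6 does not secure this in two places.

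- **Migration at 6 and 12 months.** The finding needs two post-implant images, but n asks for one. A subject with a readable later scan and no usable baseline cannot enter m under the definition, yet enters n.
- **Endoleak and patency at 1 month.** A subject with no implanted graft cannot have either event. That subject is in the analysis set, has a protocol scan under the International protocol, and so enters n.

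Such subjects are reported as event-free when they are not assessable or not at risk. The error in the At rows runs only one way, in the device's favour. SAP 7.9 makes the core lab readings the primary imaging result for the PMA and PMA-s submissions, and two programmers could reasonably build different denominators from this text.

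**Working it through.** **What the plan gives.** Neither document states an expected imaging event rate, a number of unreadable or missing images, or a number of subjects without a graft, so there is no planned imaging figure to reproduce. Only the reference sizes come from the SAP (section 6): 87 evaluable subjects at 30 days and 63 at 1 year. The 63 is stated for the MDE rate and is borrowed here as a plausible number of 12-month scans.

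**Formula.** Let u be the subjects in n who cannot enter m.

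- Rate as written: m/n
- Rate among assessable subjects: m/(n − u)
- Ratio of the first to the second: (n − u)/n

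The ratio is never above 1, so in the At rows any such subject lowers the rate, by the fraction u/n.

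**How large u might be.** For the no-graft part, the SAP expects 6% of subjects to fail the whole primary composite: 0.06 × 87 = 5.2. Access and deployment failures are only part of that, so u = 5 is about a ceiling under the plan's own assumption. For missing baselines no document figure exists, and u = 3 to 10 is a pure assumption.

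**Illustrations (m and u assumed).**

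| Endpoint | m/n as written | u | m/(n − u) | Shift, points |
|---|---|---|---|---|
| Endoleak, 1 month | 5/87 = 5.75% | 1 | 5/86 = 5.81% | 0.06 |
| | | 3 | 5/84 = 5.95% | 0.20 |
| | | 5 | 5/82 = 6.10% | 0.35 |
| Migration, 12 months | 3/63 = 4.76% | 3 | 3/60 = 5.00% | 0.24 |
| | | 6 | 3/57 = 5.26% | 0.50 |
| | | 10 | 3/53 = 5.66% | 0.90 |

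The shift grows with the event rate. At a 20% rate among assessable subjects, u = 5 of 87 gives a reported 20% × 82/87 = 18.85%, which is 1.15 points low.

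The no-graft follow-up rule is documented only for the International trial (47 subjects). There alone, 3/47 = 6.38% becomes 3/46 = 6.52% with u = 1, or 3/44 = 6.82% with u = 3.

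**Does the fallback image close the migration gap?** Its wording attaches to the expansion calculation, not to the migration call. It is also not limited to post-implant images. A pre-implant scan can serve as a diameter baseline but cannot show where the graft was.

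**Through rows.** At 1 month the Through and At definitions coincide. At 6 and 12 months the Through denominator keeps anyone with an event in any window so far, but drops a subject with clean earlier scans and no image in the current window. That pushes the rate up, against the effect described here.

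**The case against.** The best reply is that readable means readable for the finding in question. SAP Table 4 grades visibility by finding: a CT without contrast is graded visible for migration but invisible for endoleak and patency. A core lab faced with no baseline or no graft may record the finding as not evaluable. On that reading the problem disappears. But the SAP does not define the term, and it uses Table 4 only to choose between conflicting images, not to set n. The core lab guidelines and the US protocol, which the SAP names as its reference for clarification, are not among the documents reviewed.

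Several limits stand in full:

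- **Missing baselines should be uncommon.** The 1-month analysis window is days 1 to 90 (SAP Table 3), and protocol F.2.4 lets a discharge or pre-day-15 scan substitute in some cases.
- **The no-graft part rests on the International protocol.** Up to 50% of the PMA data may come from that trial; the US follow-up rule for such subjects cannot be checked here.
- **Materiality is modest.** The endpoints are secondary and descriptive, with no threshold or decision attached.

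A reader might also infer three stronger things that the documents do not support. First, that all imaging rates are biased downward: patency within 6 or 12 months fits the Through rows, where an opposite bias also operates. Second, that no-graft subjects dilute the 12-month endoleak rate: under the International protocol they leave protocol follow-up after the 1-month visit. Third, that device failures are hidden: SAP 7.9 counts access and deployment failures as failures on the primary endpoint.

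**Conclusion.** The point holds in a limited form. Table 6 states an explicit rule. Followed literally, it counts as event-free (a) subjects at 6 and 12 months with a readable scan but no usable post-implant baseline, for migration, and (b) subjects at 1 month with no implanted graft, for endoleak and patency loss. In the At rows the direction is certain whenever such subjects exist.

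The size is probably a fraction of a percentage point to about one point. That rests on assumed counts, on low event rates, and on a literal reading of readable. The primary endpoint and its test are unaffected, and no net direction is claimed for the Through rows at 6 and 12 months. The wording should be corrected before the imaging tables are programmed, but it does not threaten the trial's main conclusion.

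**What to change.** Replace the single n in Table 6 with a definition by endpoint:

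- **Endoleak and patency:** subjects with a study graft implanted and an image in the window that is assessable for that finding.
- **Migration:** the same, plus a usable post-implant baseline image. State whether the earlier-image fallback applies to migration and, if so, limit it to post-implant images.
- **Expansion:** subjects with a study graft implanted, a 1-month image or the SAP's existing fallback image, and an assessable image in the window. Requiring a 1-month image here would delete a rule the SAP already has.

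Report the number not assessable, with the reason, beside each rate. In the same edit, reconcile the text after Table 6, which uses the 12-month window for n at the 24- to 60-month visits.

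The cost is SAP wording and one denominator flag per endpoint; no new data collection is proposed. The downside is that n becomes slightly smaller and the rates slightly less favourable.

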### F.3 Data collection requirements

Clinical data will be collected preoperatively to establish eligibility, at baseline, during the index procedure, throughout the hospital stay, and postoperatively at the required follow-up visits described in Section F.2. The data collection schedule is summarized in Table F-2. Imaging for baseline and follow-up assessments, as specified in Table F.2, will be sent to a Core Lab for analysis. In addition, any interim imaging of the stent graft region done within one year of implantation should be recorded on the interim image eCRF (e.g. 6-month imaging follow-up when performed as standard of care and/or when performed further to any issue observed at previous imaging follow-up). In case further analysis is needed, procedural and interim imaging exams are to be submitted to Core Lab.

Study data will be collected using electronic case report forms (eCRFs) as will be described in Section G.1. eCRFs should be electronically reviewed and approved by the clinical investigators. Medtronic monitors will perform source document verification of the eCRFs. The monitoring strategy will be defined in the monitoring plan.

For test equipment critical for assessing endpoints (e.g., CT scan, MRI, Transesophageal echography (TEE)) maintenance and calibrations will be monitored periodically.

It is expected that the Investigator enrolling the subject at the participating site where the implantation occurred will follow the subject during the course of the study. It is the responsibility of the Investigator to make sure that the subject is followed and that integrity and accuracy of the data is maintained.

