At enrollment, those subjects who sign and date the informed consent document, meet all of the study eligibility criteria, and are approved by the IPR will be eligible for inclusion into the Valiant Evo US Clinical Trial. The subject will only be considered enrolled when arterial access is established and an attempt to introduce the Valiant Evo Thoracic Stent Graft is made. A single, primary stent graft may be used by itself if its size is sufficient to provide the desired coverage. Alternatively, it may be used in combination with additional stent graft sections that increases the graft length distally or proximally to the primary section.

The Valiant Evo Global Clinical program will be conducted under both the Valiant Evo US Clinical Trial protocol and Valiant Evo International Clinical Trial protocol, and will enroll up to 37 sites worldwide. Inclusion will be halted at sites that reach the 20% inclusion cap. There will be no minimum number of subjects for a single investigational site. Globally, a total of 100 subjects will be concurrently enrolled in the United States and outside the United States to support the primary endpoints. Up to 50% of subject data used to support PMA approval may come from subjects enrolled at sites outside of the US under the Valiant Evo International Clinical Trial protocol.

The primary endpoint analysis will be completed upon 87 evaluable subjects reaching the 30 day endpoint. The data obtained from these 87 evaluable subjects will be used to support PMA-s Approval of the Valiant Evo Thoracic Stent Graft System and to support any other future Medtronic submissions to regulatory bodies.

Subjects enrolled under the Valiant Evo US Clinical Trial require follow-up evaluations at the following time points:

- 1 month following the index procedure (30 ± 15 days)
- 6 months following the index procedure (183 ± 30 days)
- 12 months following the index procedure (365 ±60 days)
- 24 months following the index procedure (730 ±60 days)
- 36 months following the index procedure (1095 ±60 days)

- 48 months following the index procedure (1460 ±60 days)
- 60 months following the index procedure (1825 ±60 days)

Note that the 6-month follow up is not mandatory for subjects enrolled under the Valiant Evo International Clinical Trial protocol. Available 6-month follow-up data from the international trial will be used for analysis.

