k = No. of Subjects Who Had No MDE	No. of subjects who have been in study for at least 1 day and without an MDE.	No. of subjects who have been in study for at least 91 days and without an MDE.	No. of subjects who have been in study for at least 305 days and without an MDE.

If a subject is early terminated from the study, the last day that the subject has been seen will be the duration in study, which can be the day of last follow-up, last imaging taken, an AE reported, or withdrawal from the study. If a subject is still in the study, the duration in study will be the time from index procedure to the cut off day that the database is locked or data snapshot is taken.

Subgroup analyses by-sex, by-race (based on subjects enrolled in the US only, since collection of race and ethnicity data may not be allowed outside the US as per local law and regulation), FreeFlo versus Closed Web configuration as proximal component, percutaneous access versus non-percutaneous, and by-region/study site will be performed on the primary study endpoint using descriptive statistics and reviewed for

clinical significant difference.

Secondary Endpoints

30-day Secondary Endpoint

The following secondary endpoints will be evaluated within 30 days post treatment:

- Peri-operative mortality
- All adverse events (AE) within 30 days including:
 - Major Adverse Event(s) (MAE)
 - Serious Adverse Event(s) (SAE)
- Secondary procedures
- Loss of stent graft patency at 30 day visit based on imaging findings
- Endoleaks at 30 day visit based on imaging findings

Detailed definitions of MAEs are defined in the Clinical Investigational Plan Appendix L.2.2. MAEs will be identified using codes in the Medical Dictionary for Regulatory Activities (MedDRA) provided by the Medtronic Clinical Safety group.

6-month Secondary Endpoints:

The following secondary endpoints will be evaluated:

- All-cause mortality within 183 days
- Aneurysm-Related Mortality within 183 days
- MDEs within 183 days
- All AEs within 183 days including:
 - MAEs
 - SAEs
- Secondary procedures within 183 days
- Loss of stent graft patency within 6 months based on imaging findings
- Endoleaks at 6 months based on imaging findings

- Stent graft migration at 6 months as compared to 1-month imaging
- Aneurysm expansion > 5mm at 6 months based on imaging findings relative to the 1-month visit

12-month Secondary Endpoints

The following secondary endpoints will be evaluated:

- All-cause mortality within 365 days

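### Table 6 cumulative imaging rates keep every early event but drop event-free subjects not scanned in the last window, so loss of patency through 6 or 12 months tends to be overstated

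*SAP*

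**What the plan says.** SAP 7.9, Table 6, defines each imaging rate as m/n.

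- **Through 6 Months.** The numerator takes events seen on scans in the 1- or 6-month window. The denominator is "No. of subjects who had an event (counted in m) or had a readable image within the 6-month window".
- **Through 12 Months.** The numerator adds the 12-month window. The denominator is "No. of subjects who had an event (counted in m) or had a readable image within the 12-month window".

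Among the imaging endpoints in SAP 7.9, loss of patency is the one worded cumulatively: "Loss of stent graft patency within 6 months based on imaging findings" and "Loss of stent graft patency within 12 months based on imaging findings". The others are tied to the visit, for example "Endoleaks at 6 months based on imaging findings".

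On scan availability, SAP 5 says "Note that the 6-month follow up is not mandatory for subjects enrolled under the Valiant Evo International Clinical Trial protocol", and then "Available 6-month follow-up data from the international trial will be used for analysis". Protocol F.2.4 requires contrast CT or MRI at 1 and 12 months. Protocol F.3 gives as its example of interim imaging "6-month imaging follow-up when performed as standard of care and/or when performed further to any issue observed at previous imaging follow-up". The 6-month analysis window in SAP Table 3 runs from day 91 to day 304.

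SAP 7.4 allows no imputation beyond incomplete onset dates, and its optional tipping-point analysis covers only the primary endpoint. For cumulative imaging rates through 24 to 60 months, SAP 7.9 changes method: it treats image-based events as interval censored and uses survival analysis suited to that.

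**The concern.** The rule for staying in the denominator differs by outcome. An early event keeps a subject in both m and n whether or not there is a later scan. A clear 1-month scan does not keep a subject in n unless a readable last-window scan follows. Information that a subject was event-free at 1 month is discarded, while information that a subject had an event is kept.

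At 6 months the missing scans are built into the design, because nearly half of the pooled subjects have no required visit. The reported rate then depends partly on how many International subjects happen to be scanned, and not only on how the graft performs. At 12 months the scan is scheduled in both trials, so only missed or unreadable scans matter.

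A second effect is related but separate. Some International 6-month scans will be done because of an earlier imaging finding, and this could enrich the visit-specific 6-month rates for endoleak, migration and expansion. The denominator rule does not touch those endpoints.

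**Working it through.** Table 6 gives a formula and no numerical rate, so there is no stated figure to reproduce. The check is on the formula.

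**Inputs from the documents.** 47 International subjects (Protocol C.7); 100 pooled subjects (SAP 5 and 6); the Table 6 definitions.

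**Assumptions.** The other 53 subjects are US; everyone has a readable 1-month scan; event rates and scan uptake are as shown below.

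**Direction.** Let p1 be the risk of an event seen in an earlier window, p2 the last-window risk in those still event-free, and r the share of event-free subjects with a readable last-window scan.

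- Table 6 rate: R = [p1 + (1−p1)·r·p2] / [p1 + (1−p1)·r]
- True cumulative risk, if scanning is unrelated to outcome: T = p1 + (1−p1)·p2
- Ratio of event-free proportions: (1−R)/(1−T) = r / [p1 + (1−p1)·r]

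The ratio is below 1 whenever p1 > 0 and r < 1, so R exceeds T. It equals 1 if there are no early events or if scanning is complete.

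**Size at 6 months.** Take no later events (p2 = 0) and a 1-month rate e. Let g and f be the shares of event-free US and International subjects scanned. Then s = 0.53g + 0.47f and R = e / [e + (1−e)·s].

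| g | f | s | True 1% reported as | True 5% reported as |
|---|---|---|---|---|
| 1.0 | 0 | 0.530 | 0.01/0.5347 = 1.87% | 0.05/0.5535 = 9.03% |
| 1.0 | 0.25 | 0.6475 | 1.54% | 7.52% |
| 1.0 | 0.50 | 0.765 | 0.01/0.7674 = 1.30% | 0.05/0.7768 = 6.44% |
| 0.9 | 0 | 0.477 | 2.07% | 9.94% |
| 0.9 | 0.50 | 0.712 | 1.40% | 6.88% |

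The f = 0 rows are a bound. The wide window will catch some routine International scans.

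**Size at 12 months.** With 10% or 20% of event-free subjects unscanned (s = 0.9 or 0.8), 1% becomes 0.01/0.901 = 1.11% or 0.01/0.802 = 1.25%. Likewise 5% becomes 0.05/0.905 = 5.52% or 0.05/0.810 = 6.17%.

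**What would cancel the bias.** Let N = p1 + (1−p1)·r be the share of subjects kept, and u the later risk of those dropped. The true risk is N·R + (1−N)·u, which equals R only when u = R. Dropping subjects therefore amounts to giving them the whole reported rate as later risk, although they were clear at 1 month.

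Example with p1 = 5%, p2 = 1% in scanned subjects and r = 0.53:

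- R = (0.05 + 0.95 × 0.53 × 0.01) / 0.5535 = 9.94%
- T = 0.05 + 0.95 × 0.01 = 5.95% if unscanned subjects share the 1%
- The two agree only if the unscanned later risk is 9.94%, about 10 times that of scanned subjects.

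**Check of the remedy.** The interval-censored nonparametric estimate (Turnbull), on the same scenarios with e = 5% and g = 1, returns 5.00% with no later events and 5.95% with 1% later risk, both at f = 0 and at f = 0.5.

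**The case against.** The case for leaving Table 6 alone has several parts.

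- **Reach.** The SAP never says that endpoints worded as within a period use the cumulative rows. That is inferred from the wording, and by that wording only loss of patency is affected. It is descriptive. This stands, and it limits the importance of the point.
- **Rarity.** Protocol L.2.1 defines loss of patency as complete occlusion, and nothing in the documents supports a rate as high as 5%. At 1% even the bound adds less than one percentage point. Exact 95% intervals are about 0.03% to 5.4% for 1/100 and 1.6% to 11.3% for 5/100, wider than the bias. This stands as a statement of size. But sampling error does not excuse a systematic error added to it.
- **Convention and direction.** Requiring a last-window image avoids claiming patency that was not observed, SAP Table 5 uses a similar follow-up rule for major device effects, and the error runs against the device. All true. None of it makes the estimate unbiased, and core-lab imaging results are the primary ones for the PMA submissions.
- **Recovery at 12 months.** International subjects without a 6-month scan re-enter with the required 12-month scan. This stands, and is why the 12-month effect is small.
- **Limits of the remedy.** An interval-censored estimate needs a stated evaluation day and does not correct for-cause scanning. Also, Protocol F.3 sends interim scans to the core lab only if further analysis is needed, so core-lab data at 6 months may be sparser and more selected. Both stand. The first is an implementation detail; the second is a reason to show the 6-month data by trial.

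**Conclusion.** The concern holds. The cumulative rows of Table 6 use an outcome-dependent denominator, and nothing else in the SAP corrects it. The reported rate is too high whenever there are early events and some event-free subjects lack the later scan, unless the unscanned subjects' later risk is at least as high as the whole reported rate.

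The size depends on assumed inputs. In the scenarios above, a true 1% is reported as 1.3% to 2.1% at 6 months and 1.1% to 1.2% at 12 months. A true 5%, an illustrative value with no support in the documents, is reported as 6.4% to 9.9% and 5.5% to 6.2%. With no early events and scanning unrelated to outcome, there is no inflation.

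The consequence is confined to a descriptive secondary endpoint, and to any other imaging event reported with these rows. The primary test is untouched. The correction is worth making because it is cheap, and because the 12-month and 24-month cumulative figures would otherwise come from inconsistent methods.

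**What to change.** In Table 6, replace the m/n definition in the 6- and 12-month cumulative rows with the interval-censored method already specified for 24 to 60 months, using all subjects with at least one readable post-implant image. State the day at which the estimate is read (for example the Table 3 target day) and which endpoints use the cumulative rows. State also that the method assumes scan timing is unrelated to outcome: it repairs the lost denominators but not for-cause scanning.

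For that second problem, present the visit-specific 6-month rates for US and International subjects separately as well as pooled, each with its denominator.

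The cost is SAP wording and a little programming with a method already planned. No new data are needed. The by-trial tables add rows with small denominators.
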